Department Clinical Development & Medical Affairs Region Europe

Redacted Non-Interventional Study Protocol

CLCZ696B3401

Title	Assessment of Real Life cAre – Describing EuropeaN Heart
וווכ	issessificiti di Neai Life dale – Describilio Lutopean i leati

Failur E Management (ARIADNE)

Protocol version

identifier

v00 (original protocol)

Date of last

version of protocol

25 April 2016

EU PAS register

number

ENCEPP/SDPP/13835

Active substance Sacubitril/valsartan (LCZ696), Angiotensin receptor-neprilysin

inhibitors (ARNIs), ATC code C09DX04

Medicinal product and product code

EU marketing authorisation number:	Name	Strength	Packaging size
EU/1/15/1058/001	Entresto	24 mg/26 mg	28 tablets
EU/1/15/1058/002	Entresto	49 mg/51 mg	28 tablets
EU/1/15/1058/003	Entresto	49 mg/51 mg	56 tablets
EU/1/15/1058/004	Entresto	49 mg/51 mg	168 (3 x 56) tablets
EU/1/15/1058/005	Entresto	97 mg/103 mg	28 tablets
EU/1/15/1058/006	Entresto	97 mg/103 mg	56 tablets
EU/1/15/1058/007	Entresto	97 mg/103 mg	168 (3 x 56) tablets

Procedure number

EMEA/H/C/004062

Name of marketing authorization holder(s) Novartis Europharm Limited, [name]

Joint PASS

No

Research question and objectives

The main objectives of the present NIS are to provide an European picture of (i) the demographic and clinical features of symptomatic chronic heart failure patients with reduced left-ventricular ejection fraction (HFrEF) managed in the outpatient sector and the diagnostic and pharmacological interventions they receive and (ii) the demographic and clinical features of patients for whom the treating physician decided to start sacubitril/valsartan, the pattern of administration of this drug, the diagnostic and therapeutic interventions these patients receive and the safety and tolerability profile of this drug in real life.

Country (-ies) of study

List of countries is provided in stand-alone document

Author

Property of Novartis
Confidential
May not be used, divulged, published or otherwise disclosed without the consent of Novartis

NIS Protocol Template Primary Data Collection Version 2.0 dated 15-Sep-2015

Marketing authorization holder(s)

Marketing authorization holder(s)

MAH contact person

Novartis Europharm Limited, [name]

Table of contents

	Table	of conte	nts	4
	List o	f figures		5
	List o	of tables		5
1	Respo	onsible pa	arties	7
2	Abstr	act		8
3	Amer	ndments a	and updates	12

ISPE International Society for Pharmacoepidemiology KCCQ Kansas City Cardiomyopathy Questionnaire

LVAD Left-Ventricular Assist Device
LVEF Left-ventricular Ejection Fraction
MAH Marketing Authorization Holder

MedDRA Medical Dictionary for Regulatory Activities

[figure not shown]
NIS Non-Interventional Study

NP Natriuretic Peptide

NT-proBNP	N-Terminal prohormone of Brain Natriuretic Peptide
NYHA	New York Heart Association
PAS	Post-Authorization Study
PASS	Post-Authorization Safety Study
PCI	Percutaneous Cardiac Intervention
QoL	Quality of Life
RAAS	Renin-Angiotensin-Aldosterone System
SAE	Serious Adverse Event
SAP	Statistical Analysis Plan
SD	Standard Deviation
SmPC	Summary of Product Characteristics
SoC	Standard of Care
SOP	Standard Operating Procedure
STROBE	Strengthening the Reporting of Observational Studies in Epidemiology
UK	United Kingdom
WHO	World Health Organization

1 Responsible parties

Table 1-1 Main responsible parties

Page 8

CLCZ696B3401

2 Abstract

Title

Assessment of real life care – describing European heart failure management (ARIADNE)

Version and date

Version 00 (original protocol), dated 25-APR-2016

Name and affiliation of main author

Rationale and background

Although Heart Failure (HF) was responsible for approximately 1.6 million hospitalizations per year in the EU recently as judging by ICD-10 I50 coding reported by Eurostat (Eurostat 2014), comprehensive epidemiological data spanning the continent have begun to emerge only relatively recently. In Germany alone, HF was responsible for 386,548 hospitalizations and 46,410 deaths in 2012 as judging by ICD-10 I50 coding reported by the Federal Statistical Office (Statistisches Bundesamt 2013).

While the European Society of Cardiology (ESC) Long-Term Registry aims to describe the clinical epidemiology of outpatients and in-patients with HF across Europe and Mediterranean countries (Maggioni, Anker et al. 2013), a number of European countries did not enroll patients for this registry. In addition, patients treated in the outpatient sector are underrepresented in this registry. Some focused registries like EVITA-HF (von Scheidt, Zugck et al. 2014) have been conducted, but they have often focused on tertiary care centers and may therefore not be representative for the management of European HF patients who are managed by primary care physicians and office-based cardiologists. In general, registries in Europe often show an intrinsic bias toward patients cared for at scientifically interested sites (with an overrepresentation of hospital based care).

REPORT-HF, a global HF Registry sponsored by Novartis, aims to include approximately 20,000 patients worldwide, approximately 14,000 of them in Europe. However, in REPORT-HF patients are enrolled exclusively during a hospitalization for HF and data collection is focusing on the acute phase with merely telephonic follow up of patients. Thus, a prospective non-interventional study capturing chronic HF (CHF) patient management in an office-based European setting is needed in order to obtain a representative picture of CHF management in Europe. Akin to expected variations in CHF management due to national healthcare policies, regional differences e.g. depending on setting (e.g. urban vs. rural), the proximity of specialized HF or cardiology centers, and local budgetary situations, have never been systematically explored in the context of HF management.

With HF mortality remaining at unacceptably high rates, novel treatment approaches are urgently needed. Sacubitril/valsartan (also called LCZ696) constitutes the first of a new class of drugs – Angiotensin Receptor-Neprilysin Inhibitors, ARNIs – designed to replace the current role of ACE inhibitors or Angiotensin receptor blockers (ARBs) in the management of HF. In a recent phase III trial (PARADIGM-HF), sacubitril/valsartan at a target dose of 200 mg BID reduced cardiovascular mortality by 20% compared to a evidence-based dose of the ACE inhibitor enalapril (10 mg BID) (McMurray, Packer et al. 2014). While PARADIGM-HF established a superior efficacy of sacubitril/valsartan with a safety profile comparable to that of enalapril, it appears extremely important to gather additional data on its use and effectiveness in a real life setting, such as which patients are started on sacubitril/valsartan; the pattern of administration of the drug at start and the proportion of patients able to tolerate the drug at different doses; the impact on healthcare resource utilization; quality of life (QoL); main efficacy and safety events in a real-life setting with a more diverse set of patients,

The above mentioned questions will be addressed within the present prospective non-interventional study (NIS). ARIADNE will enroll and describe 12.000 symptomatic CHF patients with reduced left ventricular ejection fraction (HFrEF) treated by specialists in an office-based setting across European countries: 6000 patients treated with current standard of care (SoC) and 6000 patients on sacubitril/valsartan. Enrollment in both cohorts will start in each single country when sacubitril/valsartan is available for use in clinical practice.

Research question and objectives

The main objectives of the present NIS are to provide an European picture of (i) the demographic and clinical features of HFrEF patients managed in the outpatient sector and the diagnostic and pharmacological interventions they receive and (ii) the demographic and clinical features of patients for whom the treating physician decided to start sacubitril/valsartan, the pattern of administration of this drug, the diagnostic and therapeutic interventions these patients receive and the safety and tolerability profile of this drug in real life.

The **endpoints yielding to the primary objectives** are descriptive in nature and will be derived from the baseline demographic and medical history variables and sacubitril/valsartan treatment data.

Study design

This is an observational, European NIS with prospective collection of primary data. Data will be collected for two groups of HFrEF patients: Symptomatic patients who receive the current individualized standard of care (SoC) for the treatment of CHF and patients for whom the physician has decided to prescribe sacubitril/valsartan. The decision to prescribe sacubitril/valsartan has to be made independently from the participation in this study. This independency is ensured by the fact that patients with any CHF treatment, who satisfy the inclusion and exclusion criteria, can be enrolled. Switching between different CHF treatments (e.g. between SoC and sacubitril/valsartan) is allowed at any time as per decision of the investigator.

Enrollment will start in each country when sacubitril/valsartan is available for clinical use. Assuming that the penetration of sacubitril/valsartan into clinical practice will be slow immediately after launch, the enrollment of sacubitril/valsartan patients will take a significantly longer time than enrollment of SoC patients. At each country level the enrollment of sacubitril/valsartan patients will be continuous, while the enrollment of SoC patients will be divided into two phases, where approximately one half is immediately enrolled at the start of the study and the other half is enrolled during the last part of enrollment into the sacubitril/valsartan group.

All patients, independent of their treatment are to be enrolled consecutively, in order to avoid selection bias.

Population

ARIADNE will include consecutive adult HFrEF patients who are treated by either office-based cardiologists or selected primary care physicians (recognized as HF specialists) all over Europe.

Inclusion criteria

- 1. Written informed consent provided by the patient or legal representative for participating in the study (according to country specifications)
- 2. Age ≥ 18 years
- 3. Patients with symptomatic CHF (NYHA class II IV) with a documented reduced left ventricular ejection fraction (LVEF) as assessed by clinical examination and any imaging technique performed anytime in the past.

Exclusion criteria

- 1. Concomitant or planned participation in any interventional clinical trial
- 2. Patients who are receiving ongoing treatment with sacubitril/valsartan that has been started prior to market launch in their respective country, e.g. within a clinical trial or early access program.

- 3. Patient still within the safety follow up phase of any previous interventional or non-interventional trial using sacubitril/valsartan (LCZ696), independently whether they received sacubitril/valsartan or the comparator.
- 4. Acute decompensated HF requiring hospitalization at the moment of enrollment
- 5. Existing contraindications according to approved product information

Variables

- Demographics (age, gender, living at home or institution, relationship status, education)
- Medical history and comorbidity burden (with focus on duration of HF, etiology of CHF, last hospitalization for HF, cardiovascular conditions, specific comorbidities such as diabetes, renal insufficiency, COPD, anemia, obesity, cancer)
- Clinical Events (CV related and non-CV related deaths and hospitalizations, myocardial infarctions, cerebrovascular incidents)
- Number of visits (other than hospitalization) by provider and primary reason during follow-up
- Diagnostic and therapeutic procedures utilized during follow-up (Results will be collected only
 as available for blood potassium, blood creatinine, BNP, NT-proBNP and for
 echocardiographic EF. In all other cases, only documentation if the procedure has been
 performed and its primary reason)
- Treatment received, both pharmacological and non-pharmacological
- Vital signs and HF signs and symptoms
- Specifically for sacubitril/valsartan: dose at initiation, steps to up-titration, final dose. In case
 of lack of up-titration, of down-titration or discontinuation, the reason for it will be pursued and
 recorded in the eCRF.
- EQ-5D and Kansas City Cardiomyopathy Questionnaire (KCCQ) only in those sites where these questionnaires are part of the routine management of CHF and thus their completion does not affect the non-interventional nature of the present NIS.
- Adverse Events (AEs) and Serious AEs (SAEs), Adverse Drug Reactions (ADRs) and Serious Adverse Drug Reactions (SADRs)

Data sources

This is an observational study with prospective data collection. For some variables, retrospective data shall also be obtained from the patients' medical records (e.g. healthcare utilization in the past 12 months, medical history). The study comprises three visits: at baseline and at approximately 6 months and 12 months after baseline. No exact dates will be enforced for patient visits to avoid interference with usual care. Patients will be enrolled on a consecutive basis. Patient records at the site will be regarded as source data. Sites will be monitored, either with on site or remote monitoring.

Study size

Overall the present NIS will enroll 6000 patients on SoC and 6000 patients on sacubitril/valsartan across Europe.

Data analysis

Only descriptive data analyses will be carried out, supported by calculation of confidence intervals. No statistical testing will be performed.

Analyses will be performed for the total sample and stratified by demographic, anamnestic and medical factors (e.g. sex, duration of HF, severity of HF, previous HF-treatment), using an adequate grouping. As appropriate, analysis of all endpoints will also be carried out after stratification according to CHF treatment during the observation period.

Details on the analysis will be specified in the Statistical Analysis Plan, which will be finalized prior to any data base lock for any analysis (interim or final).

Milestones

3 Amendments and updates

None.

4 Milestones

Table 4-1 Study milestones

Milestone	Planned date
Start of data collection	
End of data collection	
Interim report	
Final report of study results	
Registration in the EU PAS register	

5 Rationale and background

Although management and therapy of chronic heart failure (CHF) have markedly improved over the last two decades, the prognosis faced by heart failure patients remains poor (Friedrich and Bohm 2007, Mozaffarian, Benjamin et al. 2016).

The prevalence of HF is on the rise because of the increasing life expectancy of the population and the long-time survival of patients with coronary artery disease (Mosterd and Hoes 2007). It is the only cardiovascular disorder that continues to rise both in incidence and in prevalence (Braunwald 2013). Approximately 1-2% of the adult European population has HF, with the prevalence rising to 10% among persons 70 years of age and older (McMurray, Adamopoulos et al. 2012).

Before the modern era of treatment in the 1990s', 60-70% of patients died within 5 years of diagnosis (McMurray, Adamopoulos et al. 2012). Mortality has since then decreased significantly, but has not levelled off anymore since the late 1990s, with a current 3-year mortality remaining above 25% for HF patients above 55 years of age (Barasa, Schaufelberger et al. 2014) and 50% at 5 years (Friedrich and Bohm 2007, McMurray, Adamopoulos et al. 2012). In spite of the introduction of new diagnostic procedures (echocardiography, NT-proBNP), of drug therapies with a proven mortality benefit and of devices such as cardiac resynchronization therapy (CRT) and implantable cardioverter defibrillator (ICD), patients with CHF still face a severe prognosis.

Several explanations for this persistently dismal prognosis are discussed:

- Randomized controlled drug trials in CHF, while showing morbidity and mortality benefits of drug therapies, have excluded important categories of patients such as the elderly with comorbidities, those with significant renal dysfunction or low blood pressure.
- Patients with comorbidities constitute a large proportion of those seen in daily practice by practitioners in the out-patient setting. A Dutch study calculated that 78% of patients older than 80 years seen by primary care physicians are multi-morbid (van den Akker, Buntinx et al. 1998). This is true for HF patients as well. The elderly and comorbid CHF patients are being managed most often by the general practitioners, who are not experts in HF management.
- Heart failure is a heterogeneous disorder, and its diagnosis can be challenging. Heart failure with preserved left ventricular ejection fraction (HFpEF) in particular constitutes a clinical challenge and requires exclusion of other diagnoses before it can be established. Primary care physicians, are less familiar with the necessary distinction between HFpEF and HFrEF making them uncertain about the proper handling of CHF overall.
- Poor drug compliance by HF patients might play a prognostic role as well, through undertreatment, suggesting that new therapeutic options may have neglected quality of life concerns (e.g. drug or device side effects) (Lainscak, Cleland et al. 2007).

Surveys, registries and HF programs have been conducted in order to evaluate compliance by physicians to recommended diagnostic procedures and HF therapy recommended by guidelines. Most registries and surveys show that diagnostic workup for CHF as well as recommended drug therapy are insufficiently applied. Most of the large European Heart

Failure registries have been conducted under the auspices of the European Society of Cardiology (ESC). The recent ESC HF Long Term Registry (Maggioni, Dahlstrom et al. 2013) showed that only 30% of patients receive the target dosage of the drugs recommended by guidelines, but only in two out of three patients, reasons for not reaching target doses were provided (doctor's uncertainty, patient refusal, logistical or cost issues). A more refined understanding of the management of CHF in Europe is hampered by the fact that most large registries, those of the ESC in particular, have recruited from tertiary centers and that in general they mix acute and chronic HF patients. Insufficient data are available about management of CHF in the outpatient sector where a large number of HF patients are managed. HF is a difficult diagnosis for primary care physicians to establish accurately (Hobbs, Doust et al. 2010). The recommended work up with echocardiography and/or BNP or NT-proBNP seems to be performed in only a fraction of the patients in routine primary care physicians' practice, for example in the UK (Hobbs, Doust et al. 2010) or in Sweden (Dahlstrom, Hakansson et al. 2009). Similar to the situation in tertiary centers, adherence to therapeutic recommendations is insufficient in the primary care setting (Calvert, Shankar et al. 2009, Dahlstrom, Hakansson et al. 2009). Adherence to HF recommendations by office-based cardiologists has hardly been studied, though some data suggest improvement is achievable (Fonarow, Albert et al. 2010).

Observing how difficult it is for physicians to reach the recommended target doses of the prognosis-modifying HF drugs has led experts to even question the relevance of current treatment recommendations. A concept of target effect, as opposed to target dose-guided therapy is being suggested (Tavazzi, Maggioni et al. 2013). For the primary care sector taking care of elderly comorbid CHF patients, a Scandinavian team suggests to consider 50% of the recommended target dose of CHF drugs as optimal (Dahlstrom, Hakansson et al. 2009).

Although some insights about the situation in the outpatient sector are available, for the UK or Scandinavia mostly, there is a need for additional real-life data about HF management in the outpatient healthcare sector across a larger variety of European countries.

Receptor-Neprilysin Inhibitor (ARNI), has shown remarkable mortality benefit in patients with CHF (McMurray, Packer et al. 2014). Angiotensin receptor blockade (valsartan) is specific and competitive at the angiotensin type 1 (AT1) receptor, which mediates the deleterious effects of angiotensin II on the CV system. The effects of neprilysin inhibition are attributed to the enhanced effects of biologically active natriuretic peptides (NPs). Natriuretic peptides promote natriuresis and vasodilatation by counteracting the renin angiotensin aldosterone system (RAAS) and the sympathetic nervous system and exert direct antifibrotic and antihypertrophic effects on cardiomyocytes (Levin, Gardner et al. 1998, Gardner, Chen et al. 2007, Pandey 2008).

The PARADIGM-HF study was a randomized, double-blind, Phase III outcome trial that evaluated the efficacy and safety of sacubitril/valsartan (at a target dose of 200 mg BID) versus the ACEI enalapril (10 mg BID) in 8,436 HFrEF patients (McMurray, Packer et al. 2014). The primary endpoint was time to first occurrence of either cardiovascular (CV) death or heart failure hospitalization. Sacubitril/valsartan was proven to be superior to the evidence-based dose of enalapril in reducing cardiovascular mortality by 20% and hospitalizations for HF by 21%.

Based on the above described discrepancies between controlled clinical trials and the real-life clinical routine, the present non-interventional study will specifically focus on the outpatient sector, aiming at providing a clear picture of the demographic and clinical characteristics of CHF patients, how they are treated and managed overall, and how sacubitril/valsartan will fit into the day-to-day CHF management in Europe.

6 Research question and objectives

The present non-interventional study will aim to provide a Europe-wide picture of (i) the demographic and clinical features of HFrEF patients managed in the outpatient sector and the diagnostic and pharmacologic intervention they receive; (ii) the demographic and clinical features of patients the treating physician decided to start sacubitril/valsartan, the pattern of administration of this drug, the diagnostic and therapeutic intervention these patients receive and the safety and tolerability profile of this drug in real life.

Main objectives:

- To describe the profile of patients initiated on sacubitril/valsartan and patients continued on SoC in the outpatient sector in terms of demographics, medical history, HF status, comorbidity burden
- To describe the profile of sacubitril/valsartan patients not reaching and maintaining the target dose of 200 mg twice daily in terms of demographics, medical history, HF status, comorbidity burden as compared with patients reaching the target dose

Additional objectives:

- To describe the overall HFrEF population managed in the outpatient sector in Europe in terms of demographics, medical history, comorbidity burden and previous cardiovascular (CV) events rate
- To describe HF-treatment (pharmacological and non-pharmacological) in the outpatient sector in Europe and in individual countries/country clusters
- To describe the starting dose, titration and maintenance dose of sacubitril/valsartan in patients with different anamnestic and demographic characteristics
- To assess the rates of major HF related outcomes (death, hospitalizations, major CV events)
- To describe Healthcare Resource Utilization in HFrEF patients managed in the European routine practice
- To describe safety and tolerability features of sacubitril/valsartan in real-world HF patients
- To describe the quality of life (QoL) during follow-up (only in those sites where the EQ-5D and/or KCCQ QoL questionnaires are part of routine CHF management)
- To describe the levels of BNP / NT-proBNP (only if these measurements are available or at sites where these measurements are performed within the routine CHF management)

7 Research methods

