7.2 Setting

7.2.1 Population

The present study will include consecutive HFrEF patients treated by office-based cardiologists or selected primary care physicians (recognized as HF specialists) across Europe.

The study will include overall 6000 patients on SoC and 6000 patients on sacubitril/valsartan.

Considering that the different local regulations on patient management and reimbursement can significantly impact clinical practice, patient numbers will be allocated to bigger countries and/or clusters of smaller countries with similar healthcare systems in order to ensure the representativeness of the sample.

Enrollment will start in each country when sacubitril/valsartan is available for clinical use. Assuming that the penetration of sacubitril/valsartan into clinical practice will be slow immediately after launch, the enrollment of sacubitril/valsartan patients will take a significantly longer time than including SoC patients. At each country level the enrollment of sacubitril/valsartan patients will be continuous, while the enrollment of SoC patients will be divided into two phases, where approximately one half is immediately enrolled at the start of the study and the other half is enrolled during the last part of enrollment into the sacubitril/valsartan group (see Figure 7-1). By structuring the enrollment of SoC patients in this two-wave pattern, the possibility is created to compare the baseline demographic and medical characteristics of patients that drive the choice of physicians toward individualized SoC or sacubitril/valsartan (main objective) and see if their approach changes over time, after the launch of sacubitril/valsartan.

LCZ696 launch in Country A ~ 50 % ~ 50 % SoC SoC 100% LCZ696 Phase 2 Phase 1 Phase 3 12 months В ~ 50 % ~ 50 % LCZ696 launch in Country SoC SoC 100% LCZ696 Phase 1 Phase 2 Phase 3 12 months S ~50 % ~ 50 % LCZ696 launch in Country SoC 100% LCZ696 Phase 1 Phase 2 Phase 3

Figure 7-1 Enrollment schedules (examples) on single country level

Overall enrollment: 24 months

Enrollment schedule for each country will depend on enrollment numbers in SoC and sacubitril/valsartan groups and thus might need to be divided into phases, where SoC enrollment is split up in two phases, while LCZ696 enrollment is continuous (examples A-C). SoC = standard of care, LCZ696 = sacubitril/valsartan

12 months

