7.7 Data analysis

All analyses will be performed by the designated CRO.

Only descriptive data analyses will be carried out, supported by calculation of confidence intervals. No statistical testing will be performed.

The two patient populations will be considered and analyzed separately. The SoC group will allow the representative picture of current CHF management as mentioned above. The Sacubitril/valsartan stratum will provide early insight into the adoption of this new therapy, once it will be available in the different countries. Therefore also strata for patients switching between SoC and Sacubitril valsartan will be analyzed upon adequate subgrouping.

The two studied groups, SoC and sacubitril/valsartan, are expected to differ significantly depending on the progressive adoption of sacubitril/valsartan by the prescribers – this will be assessed by stratified analysis according to the above described enrollment phases. In addition, besides baseline characteristics of the patients leading to the physicians' decision to prescribe sacubitril/valsartan or continue SoC, no inferences can be made from the comparison of the characteristics of both populations. For the same reason, no comparison of data obtained during the follow-up phase between the treatment groups is planned. Similarly, no safety comparisons will be performed between SoC (where in most cases an established therapy is merely continued) and sacubitril/valsartan (where a new therapy is prescribed).

Analyses will be performed for the total sample and stratified by demographic, anamnestic and medical factors (e.g. sex, duration of HF, severity of HF, previous HF-treatment) using an adequate grouping. Similarly, data will be also analyzed stratified according to enrollment phase (phase 1 and phase 3) and treatment group (e.g. SoC, valsartan/sacubitril, switching between both groups).

The Statistical Analysis Plan will be created as a separate document prior to data base lock for any analysis (e.g. interim analyses, final analysis). This document will contain sufficient details to enable the generation of the analysis of the NIS and specifies:

- the statistical database underlying the evaluation, including all adjustments, implementations and the calculation of derived variables,
- the detailed establishment of the analyzed population(s), and
- the statistical procedures.

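### The pooled SoC versus sacubitril/valsartan baseline comparison cannot separate what drives a physician's choice from which site or physician type the patient attends

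*Protocol*

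**What the plan says.** The Abstract (Population) and section 7.2.1 admit two kinds of enrolling physician into one study population: patients are "treated by either office-based cardiologists or selected primary care physicians (recognized as HF specialists) all over Europe".

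Section 7.2.1 fixes the totals: "The study will include overall 6000 patients on SoC and 6000 patients on sacubitril/valsartan". It distributes them geographically: "patient numbers will be allocated to bigger countries and/or clusters of smaller countries with similar healthcare systems". The enrollment schedule is also run by country: "At each country level the enrollment of sacubitril/valsartan patients will be continuous, while the enrollment of SoC patients will be divided into two phases". Section 7.9 confirms that the SoC group is closed to enrollment in phase 2, while section 7.2.1 keeps the sacubitril/valsartan group open throughout.

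Section 7.2.1 then says that the two SoC waves make it possible to compare the baseline characteristics of "patients that drive the choice of physicians toward individualized SoC or sacubitril/valsartan (main objective". Section 7.7 warns against drawing inferences from comparing the two populations, but exempts the baseline characteristics that lead to the prescribing decision. The planned analyses in 7.7 are "stratified by demographic, anamnestic and medical factors", and further by enrollment phase and treatment group.

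The variables in section 7.3 do not include the enrolling physician's specialty. The nearest items are visits by type of provider during follow-up, and the referral pathway, which is collected only for patients under the investigator's care for less than six months.

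**The concern.** What leads a physician to choose one treatment over another is a question about patients of the same physician. The planned comparison pools across sites and physician types. If the groups draw on sites or physician types in different proportions, and those sites see different patients, the groups will differ at baseline even where no physician takes the characteristic into account.

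Nothing in the protocol balances that mix. Allocation stops at the country or cluster, and a site that is active mainly in phase 2 contributes mostly or only sacubitril/valsartan patients. With 6000 per group the confidence intervals are narrow, so a difference due to mix could be reported as a precise finding about prescribing. Section 7.9 discusses consecutive enrollment, the two SoC waves and patient-level confounders, but not this.

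**Working it through.** **The plan's own precision (section 7.5).** For a proportion at p = 0.5, the 95% half-width is 1.96 × √(0.25/n).
- n = 6000: 1.27 points, length 2.53 (plan: ±1.3, length 2.6).
- n = 3000: 1.79 points, length 3.58 (plan: ±1.8, length 3.6).

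For a mean, 1.96/√6000 = 0.0253 SD (plan: 0.025). The figures reproduce after rounding. They describe sampling error only.

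**Precision of a difference, 6000 per group.** 1.96 × √(2 × 0.25/6000) = 1.79 points at most.

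**Gap from mix alone.** With no selection on the trait within any practice:

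gap (SoC minus sacubitril/valsartan) = (difference in primary-care share between groups) × (difference in trait prevalence between physician types).

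It exceeds 1.79 points once the product passes 0.018, for example 13.4 × 13.4 points, or 20 × 10 points (2.0). At 10 × 10 points it is 1.0 and does not.

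**Illustrations.** The totals (12,000 patients, 6000 per group) come from the protocol. The primary-care share, the uptake and the trait prevalence do not; all three are assumed. The trait is set at 20% of cardiologists' patients and 40% of primary-care patients.

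| Primary care, of 12,000 | Of these, on sacubitril/valsartan | Primary-care share, SoC v sacubitril/valsartan | Trait, SoC v sacubitril/valsartan | Gap |
|---|---|---|---|---|
| 4800 (40%) | 20% = 960 | 64% v 16% | 32.8% v 23.2% | 9.6 |
| 6000 (50%) | 40% = 2400 | 60% v 40% | 32.0% v 28.0% | 4.0 |
| 6000 (50%) | 45% = 2700 | 55% v 45% | 31.0% v 29.0% | 2.0 |
| 1200 (10%) | 20% = 240 | 16% v 4% | 23.2% v 20.8% | 2.4 |
| 1200 (10%) | 40% = 480 | 12% v 8% | 22.4% v 21.6% | 0.8 |

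First row: 3840/6000 = 64% and 960/6000 = 16%; 0.48 × 20 points = 9.6. Last row: 720/6000 = 12% and 480/6000 = 8%; 0.04 × 20 points = 0.8, inside ±1.8. Over a wider assumed grid (share differing by 10 to 40 points, trait by 5 to 30) the gap runs from 0.5 to 12 points.

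**What stratifying costs.** Assume primary-care shares of 30% in SoC and 10% in sacubitril/valsartan, and a trait in 60% of primary-care and 40% of cardiology patients. The pooled profile shows 46% v 42%, a gap of 4.0 points (95% CI 2.2 to 5.8) due only to mix. Within physician type the gap is zero, with half-widths of ±4.5 points in primary care (1800 v 600 patients) and ±2.0 in cardiology (4200 v 5400). Standardised to a common mix, the half-width is ±1.8.

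**The case against.** The strongest reply is that the study is descriptive. Section 6 and section 7.5 speak of describing profiles, and section 7.7 analyses the populations separately without testing. A pooled profile is a correct account of who receives each treatment, and differences in uptake between physicians are part of real-world prescribing. This stands for the profiles themselves. It does not cover the reading in 7.2.1, nor the exemption in 7.7, which go beyond description.

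Second, the patient strata in 7.7 are examples, and a statistical analysis plan that is not shown could add physician type. That stands: the missing stratum alone is no finding. What the protocol does fix is the interpretation of the pooled comparison.

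Third, all patients are to be enrolled consecutively whatever their treatment, so in phases 1 and 3 a site using both treatments should contribute to both groups. This limits the imbalance. It does not help in phase 2, or at sites that use only one treatment. The stand-alone enrollment description document listed in Annex 1 is not shown and may also add detail.

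Two stronger readings are tempting. A reader might infer from section 5, which says that "The elderly and comorbid CHF patients are being managed most often by the general practitioners", that the protocol itself shows the two enrolling types to have different patients. It does not: the same sentence calls those practitioners non-experts in heart failure, whereas the primary care physicians enrolled here are selected as specialists in it. A reader might also fault the absence of the background factors named in the Abstract, "regional differences e.g. depending on setting (e.g. urban vs. rural), the proximity of specialized HF or cardiology centers". They belong to no stated objective, so leaving them unrecorded contradicts nothing.

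**Conclusion.** The point holds as a limit on interpretation. As planned, the pooled SoC versus sacubitril/valsartan comparison cannot support a statement about what drives the physician's choice, because site and physician-type mix is neither balanced nor separated out.

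The size cannot be established from the protocol. On an assumed 20-point trait difference it is under 1 point with 10% primary care and 40% of those patients on sacubitril/valsartan. It is 2.0 to 9.6 points with 40 to 50% primary care and uneven uptake, against about ±1.8 points of sampling error. A high primary-care share is itself an assumption; if few such sites enrol, or if the two types see similar patients, the physician-type effect may be negligible. The stated precision is correct and the pooled profiles stand as description. This is a worthwhile, inexpensive improvement rather than a flaw that undermines the study.

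**What to change.** - Section 7.3: record the enrolling physician's specialty once per site. Site should already be identifiable from eCRF entry, and physician type is part of how sites are chosen.
- Section 7.7: show the first main objective's profiles by physician type. Report each group's physician-type mix and the number of sites that enrolled only one group.
- Section 7.7: beside the pooled profiles, give the SoC minus sacubitril/valsartan difference within site, averaged over sites with both groups, or else standardised to a common physician-type mix. The within-site version also removes differences between sites of the same type; the standardised version does not. Base any statement about what drives choice on this contrast only.
- Section 7.9: name the issue as a limitation.

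The cost is one item per site and one extra set of tables, with no added patient procedures. The downside is that single-group sites drop out of the within-site contrast, so its confidence intervals are wider.
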